Treatment Protocol for Teriparatide: Patients with low bone turnover will receive a starting dose of 20 µg teriparatide per day via subcutaneous injections along with 30 mg of cinacalcet p.o. daily in the evening will be added after two weeks if PTH is greater than 200 pg/mL at the first biweekly lab draw. Teriparatide treatment alone in patients with histologically proven low turnover bone disease did not result in an increase in bone formation markers.²⁵ Concomitant treatment with cinacalcet is needed in these patients when intact PTH is above 200 pg/mL. To monitor control of PTH and serum calcium levels we will measure them initially one week +/- 3 days after treatment then at the biweekly monitoring visits at the CCTS and quarterly thereafter. Teriparatide dosage will be adjusted according to changes in serum calcium. If serum calcium is between 10.2 and 11 mg/dL, frequency of injection will be reduced to 5 of 7 days per week (non-injection days should not be consecutive and blood draws for serum calcium should be the morning after an injection day). A follow-up visit with serum calcium check will be scheduled in two weeks +/- 3 days. If at that time calcium levels are still between 10.2 and 11, patients will remain with injections on 5 of 7 days per week. If calcium levels return to below 10.2 mg/dL, daily injections will be reinstated and quarterly calcium checks will be performed. If serum calcium is greater than 11.0 mg/dL, treatment will be withheld for two weeks at which time serum calcium will be rechecked. If it is between 10.2 and 11.0 mg/dL we will reinstitute treatment at the reduced frequency of 5 of 7 days per week. If calcium remains above 11.0 mg/dL, patients will be referred to their primary nephrologist for workup of their hypercalcemia and excluded from further participation in the study.

To assess response or compliance to teriparatide, BSAP (see Table 2) will be measured bi-weekly until steady-state and quarterly thereafter. If results do not increase at least 8% (largest inter-assay error of this marker) the study coordinators will carefully review with the patients the technique of injections and possible compliance lapses. There are no known critical levels indicating undesirably high response without concomitant hypercalcemia. Patients, and if needed a caregiver, will be trained in the subcutaneous administration of teriparatide according to the manufacturer's guidelines.

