Table 2. Detail of Blood Draws for Monitoring Safety and Compliance and Secondary Endpoint Serum Biochemical Parameters
Teriparatide

Treatment Group Base-line Bi-weekly visits until steady state Q1 Visit Q2 Visit Q3 Visit 1 Year 15 mo 18mo 21mo 2 yr
or Safety: Serum Calcium & PTH X X X X X X X X X X X X

For Compliance: BSAP X X X X X X X X X X

Secondary Endpoints: FGF23, P1NP, Sclerostin, DKK-1 & PTH Ratio X X X X X

Alendronate

Treatment Group Base-line Monthly visits until steady state Q1 Visit Q2 Visit Q3 Visit 1 Year 15 mo 18mo 21mo 2yr

For Safety and Compliance: BSAP X X X X X X X X X X

Secondary Endpoints: Serum Calcium, PTH & PTH Ratio, FGF23, P1NP, Sclerostin, DKK-1 X X X X X

Standard of Care Controls Base-line Q2 Visit 1 Year 15mo 18mo 21mo 2 yr

Secondary Endpoints: All of the above Serum Biochemical Parameters X X X X X

Cinacalcet will be adjusted in 30 mg steps up to a maximum daily dose of 180 mg if needed to keep intact PTH at levels less than 200 pg/mL. If by six weeks, this fails to achieve PTH levels less than 200 pg/mL, patients will be excluded from further study participation. In the rare case where PTH level maintenance requires cinacalcet doses that induce serum calcium levels below 8.5 mg/dL, treatment will cease for two weeks after which calcium will be re-measured. At two weeks if calcium remains below 8.5 mg/dL, patients will be excluded from further participation in the study. If calcium is normalized, cinacalcet will be reinstated at half of the prior dose. Calcium will be checked again at the next monitoring visit. If at any measurement point PTH levels are less than 60 pg/mL cinacalcet will be withheld and reinstated if levels are again above 200 pg/mL.

Treatment Protocol for Alendronate: Patients with normal or high bone turnover will receive a starting dose of 35 mg alendronate p.o. once per week. Patients will be carefully instructed to follow the manufacturer's recommendations for administration. Serum calcium will be rechecked 1 week +/- 3 days after starting therapy. Dosage will be adjusted according to changes in the bone turnover marker

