Teriparatide for patients with low bone turnover: Patients with increased baseline risk of osteosarcoma will be excluded from this study (Paget's disease of bone, pediatric populations and young adults with open epiphyses, or prior external beam or implant radiation therapy). Our inclusion/exclusion criteria eliminate all of these patients. There are no direct contraindications given for CKD patients given in the package inserts and the safety web page. However, because bone loss with CKD-5D is not specifically addressed in the indications, we have obtained an IND (Investigational New Drug) from the FDA.

If during the monthly monitoring calls/visits or quarterly visits patients complain of new onset adverse reactions such as arthralgia, pain, nausea, dizziness or leg cramps, the patients will be counseled regarding standard treatment measures. Follow-up contact will be made in one week and if symptoms persist, treatment will be discontinued until the next regularly scheduled quarterly monitoring visit. Follow-up communication will occur within 1 week +/- 3 days and if problems persist despite discontinuation, patients will be referred to his/her primary care provider.

If patients complain of injection site reactions, they will be counseled regarding their injection technique and follow-up contact will be made in one week +/- 3 days. If reactions persist, treatment will be discontinued until next regularly scheduled quarterly monitoring visit. If problems persist despite discontinuation, patients will be referred to his/her primary care provider and their participation in the study will end.

In the rare case where PTH level maintenance requires cinacalcet doses that induce serum calcium levels below 8.5 mg/dL, treatment will cease and patients will be excluded from further participation in the study.

Alendronate for patients with normal or high bone turnover: Our inclusion/exclusion criteria cover all of the above-mentioned contraindications. To be safe, we have obtained an IND from the FDA.

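### The two rules for low calcium on cinacalcet conflict for patients who recover, and five stopping rules end study participation in treated patients only, before the 12-month hip QCT

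*Combined protocol and SAP*

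**What the plan says.** The protocol handles low calcium on cinacalcet twice.

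In Research Procedures, within the teriparatide treatment protocol (after Table 2): "In the rare case where PTH level maintenance requires cinacalcet doses that induce serum calcium levels below 8.5 mg/dL, treatment will cease for two weeks", and calcium is then measured again. Two outcomes follow. For calcium that has not recovered, the text reads: "At two weeks if calcium remains below 8.5 mg/dL, patients will be excluded from further participation in the study". For calcium that has recovered, it reads: "If calcium is normalized, cinacalcet will be reinstated at half of the prior dose", and "Calcium will be checked again at the next monitoring visit".

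In Safety Precautions, in the paragraphs on teriparatide for low turnover, the sentence opens identically but ends differently. If holding PTH down needs "cinacalcet doses that induce serum calcium levels below 8.5 mg/dL, treatment will cease and patients will be excluded from further participation in the study", that is the whole instruction.

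Four further rules end study participation in treated patients:

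- High calcium on teriparatide: "If serum calcium is greater than 11.0 mg/dL, treatment will be withheld for two weeks at which time serum calcium will be rechecked". "If calcium remains above 11.0 mg/dL, patients will be referred to their primary nephrologist for workup of their hypercalcemia and excluded from further participation".
- Uncontrolled PTH on teriparatide with cinacalcet: "If by six weeks, this fails to achieve PTH levels less than 200 pg/mL, patients will be excluded from further study participation".
- Injection-site reactions that persist even after teriparatide is stopped (Safety Precautions, teriparatide).
- Gastrointestinal symptoms on alendronate that settle and then return after restart (Safety Precautions, alendronate). This rule names the stop of drug and the end of participation as two separate acts.

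The Primary Endpoint text compares change in total hip QCT BMD between treated and control patients at one and two years. Specific Aim #1 places QCT scans at baseline, 6 months, one year and two years. Controls receive standard of care.

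**The concern.** Two matters of unequal weight are involved.

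The first is operational. A coordinator whose patient has a low calcium that returns to normal has two current instructions that cannot both be followed.

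The second concerns the primary comparison. Each of the five rules is triggered by how a patient responds to or tolerates study drug. If meeting the rule ends participation, that patient's later hip scans are lost. Randomisation made the treated and control groups comparable at baseline, but the treated patients still measured at 12 months would be a subset filtered by response or tolerance, set against controls who passed through no such filter. A difference in hip BMD change could then partly reflect who was left to measure.

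**Working it through.** No figure in the plan bears on this point, so the check compares the texts and then asks what could be computed.

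**Step 1. The two low-calcium rules side by side.**

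| Course of calcium | Research Procedures | Safety Precautions |
|---|---|---|
| First value below 8.5 mg/dL | Treatment stops, remeasure at two weeks | Treatment stops; exclusion follows, timing not stated |
| Still below 8.5 at two weeks | Excluded | Excluded |
| Normal at two weeks | Cinacalcet restarted at half dose, patient stays | Excluded, no recheck or restart |

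Only the last row conflicts.

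**Step 2. Rules sorted by what they end.**

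- End participation: persistent calcium above 11.0 mg/dL, PTH not below 200 pg/mL by six weeks, low calcium, persistent injection-site reactions (teriparatide, 4); recurrent gastrointestinal symptoms (alendronate, 1). Total 4 + 1 = 5.
- Pause or stop drug only: BSAP below the safety threshold on alendronate; arthralgia, pain, nausea, dizziness or leg cramps on teriparatide; musculoskeletal pain on alendronate.
- Controls: none in the supplied text. Their part of Table 2 lists draws for secondary endpoints and has no safety row.

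The protocol thus already separates leaving drug from leaving the study, and these five are worded as leaving the study.

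**Step 3. Timing against the scans.** The first post-baseline QCT is at 6 months. A patient removed under the six-week PTH rule leaves before it and has no post-baseline hip scan. A patient removed between months 6 and 12 may have the 6-month scan but not the 12-month one.

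**Step 4. What a size would need.** Let p be the share of the treated group removed, and d the mean 12-month hip BMD change in retained minus removed patients. The true treated mean is (1 − p) × retained + p × removed, so the retained-only mean differs from it by p × d. The documents give neither p nor d, nor the sign of d. For scale only, with assumed values of p from 5% to 30% and |d| from 0.25 to 0.5 SD, the shift runs from 0.05 × 0.25 = 0.0125 SD to 0.30 × 0.5 = 0.15 SD, in either direction.

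**Step 5. Calcium check after a half-dose restart.** It falls at the next monitoring visit. In the biweekly phase that is two weeks; in the quarterly phase it could be up to about 52 / 4 = 13 weeks, unless a restart returns the patient to biweekly visits, which the text does not say.

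**The case against.** The two low-calcium texts agree on most of the path. Safety Precautions could be a condensed restatement, since it also leaves out the high-calcium and six-week PTH rules. This limits the conflict but does not remove it: the neighbouring paragraph on injection-site reactions spells out a staged hold, so that section does state holds where it intends them. A reader might infer that the two texts give wholly opposite orders, or that Safety Precautions requires exclusion at the first low value. Neither is supported. The conflict is confined to patients who recover, and no timing is given.

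Untreated controls cannot meet drug-intolerance rules, so the absence of control triggers is inherent, and a count of 4, 1 and 0 does not measure bias. Several triggers are also narrow: low calcium is called rare, and high-calcium and injection-site exits need the problem to persist after drug is stopped. All of that stands. What it does not justify is ending measurement, as distinct from drug, in one randomised group.

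The supplied text is incomplete. Some pages were removed, and the attached study-design and procedures figures are not shown. A reader might infer that the plan has no analysis population or missing-data method. That cannot be concluded; none appears in what was supplied. Even a good analysis rule elsewhere would not recover scans that were never taken.

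A reader might also infer that the six-week PTH rule stops titration before the 180 mg maximum can be tried. The interval between dose steps is not stated, and weekly steps could reach 180 mg within six weeks, so no error is shown.

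**Conclusion.** The point holds in two parts.

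First, the low-calcium rules conflict for patients whose calcium recovers within two weeks. Because the event is described as rare, this is mainly a matter of safety and consistent conduct and should move few patients.

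Second, five treated-group rules end study participation, so as written the treated patients with a 12-month hip QCT are selected on response or tolerance. This matters more for the primary comparison. It rests on reading exclusion from participation as the end of scans, which the drug-only wording of the neighbouring rules supports, and on the supplied text containing no instruction to scan patients who have been removed.

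A reader might infer that the result is biased in favour of treatment, or by a known amount. The documents support neither, because the share removed and how those patients' bone would have changed are unknown. The 6-month scan softens the loss for late leavers only. The sponsor should change the text; the reason is the mechanism, not an estimated effect.

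**What to change.** 1. **Use one low-calcium rule in both places.** The Research Procedures version (hold two weeks, recheck, restart cinacalcet at half dose if normal) is more detailed, keeps more patients, and mirrors the hold-and-recheck used for calcium above 11.0 mg/dL. If it is adopted, add a calcium check two weeks +/- 3 days after restart, the interval already used after a reduction in teriparatide frequency. Its downside is re-exposure to half-dose cinacalcet of patients whom Safety Precautions would have removed, so the sponsor should confirm the choice.

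2. **Separate stopping drug from leaving the study.** Add one sentence governing all five rules, including the low-calcium one: a patient who meets a stopping rule stops study drug, stays in follow-up, has the planned 6- and 12-month hip QCT if willing, and is analysed in the group to which he or she was randomised. Every safety reason for stopping drug is kept.

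The cost is a protocol amendment, the already planned scans for patients who would otherwise have left, and one extra calcium draw per half-dose restart.

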Patients consenting for baseline measurements will have BMD measurements of the total hip, lumbar spine and radius by DXA and total body scan. We do not use QCT for initial BMD assessment to avoid unnecessary radiation exposure to patients with normal bone mass who will be excluded from the study. Patients who are not do not have low bone densityosteoporotic by DXA T-scores/Z-

scores at any site will be excluded from further participation. Results from our prior funding period study indicate this will be 30% or 178 patients. Those patients who are identified as having low bone density/osteoporotic will have blood draws performed for determination of turnover status (PTH, PTH ratio and TRAP-5b; see Table 1) and baseline biochemical results (serum calcium and BSAP). They will also have BMD measurements of the total hip and spine by QCT, and CAVC measured by MDCT. Patients will be assigned to one of two treatment arms based on their turnover status: 1) low turnover patients and 2) normal or high turnover patients. For each treatment arm we will use adaptive randomization by group completion rates, age race and gender to assign patients to one of two groups A) treatment, and B) no study treatment (standard of care) controls.

For the extension of treatment modification, we will contact all patients who completed one year in either the treatment or control arms. Patients who previously participated in the treatment arm will be offered an additional 1 year of therapy to complete 2 years of therapy. For patients who previously participated in the control arm, they will be offered 2 years of therapy. Both therapies can be given in two consecutive years, or with a time-gap in-between.

TREATMENT PROTOCOLS:

Low Turnover Groups: Patients with low bone turnover will be randomized to receive daily teriparatide injections with cinacalcet or no study treatment, i.e. standard of care, as controls.

Normal or High Turnover Groups: Patients with normal or high bone turnover will be randomized to receive alendronate or no study treatment, i.e., standard of care, as controls. Teriparatide is not justified in these patients because it might worsen underlying high turnover abnormalities and requires avoidable daily injections.

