BSAP from blood drawn at monthly monitoring visits for the first 3 months, thereafter at quarterly monitoring visits. BSAP is expected to go down, but to avoid over-suppression, will not be allowed to go below the low normal range of the assay, as is done clinically. Our data show that mid/normal ranges of these markers in CKD-5D patients indicate low turnover^{48, 49} If this safety threshold is crossed, treatment will be stopped until values are back above the threshold at a regularly scheduled monitoring visit. Once demonstrably back within safety threshold, treatment will be reinstated at half of the initial dose (35 mgs every other week). If BSAP does not go down at least 8% over a one month period, treatment doses will be doubled to 70 mgs per week. If they still remain high, study coordinators will carefully review with the patients the mode of drug intake and possible compliance lapses.

Primary Endpoint At one year after baseline, we will assess bone mass using QCT BMD measurements of the total hip and compare 1 and 2 year changes in bone mass between the treatment and control groups. Total hip will be used as the primary endpoint site because in our prior funding period we showed that changes at the total hip in QCT BMD are more pronounced than at the spine⁶. The Secondary endpoint will be differences between the treatment and control groups in changes in coronary artery calcifications by MDCT. This will be relevant regardless of bone effects.

Other secondary endpoints tracked at baseline, 6 months, and 1 year, 18 and 24 months will include serum biochemical markers of bone activity; FGF 23, BSAP, TRAP5b, P1NP, Sclerostin, and DKK1.

Additionally we will record 1) Change in QCT BMD of the spine to compare with the hip) 2) Changes in DXA BMD of the hip and spine (to determine whether the more commonly available DXA results are equivalent to QCT and 3) Changes in aortic and heart valve calcification (to compare with the coronary artery calcifications).^{50,51} 4) Whole body composition (%fat vs %lean) as it relates to survival in CKD-5D patients.

Attachments

Attach Type	File Name
ResearchProcedures	figure 3 7.22.2019 pdf.pdf

Data Collection: List the data or attach a list of the data to be collected about or from each subject (e.g. interview script, survey tool, data collection form for existing data).

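### Low calcium on study cinacalcet has two incompatible rules: one retains a patient whose calcium recovers, the other excludes that patient

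*Combined protocol and SAP*

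**What the plan says.** Two sections address serum calcium below 8.5 mg/dL caused by the cinacalcet dose needed to control PTH. Both open with the same clause, and both describe the event as rare.

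- **Research Procedures** (the cinacalcet paragraph after Table 2): "treatment will cease for two weeks after which calcium will be re-measured". Then: "At two weeks if calcium remains below 8.5 mg/dL, patients will be excluded from further participation in the study". Otherwise: "If calcium is normalized, cinacalcet will be reinstated at half of the prior dose", followed by "Calcium will be checked again at the next monitoring visit".
- **Safety Precautions** (Teriparatide for patients with low bone turnover): where the dose would "induce serum calcium levels below 8.5 mg/dL, treatment will cease and patients will be excluded from further participation in the study". This sentence mentions no hold period, re-measurement, restart or later check, and does not refer back to Research Procedures.

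The rule concerns one randomized group. Low-turnover patients are "randomized to receive daily teriparatide injections with cinacalcet or no study treatment, i.e. standard of care, as controls". Within the treated group it reaches patients given study cinacalcet: "Concomitant treatment with cinacalcet is needed in these patients when intact PTH is above 200 pg/mL". The primary comparison follows later: "At one year after baseline, we will assess bone mass using QCT BMD measurements of the total hip".

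**The concern.** The trigger and threshold are identical, but one section makes exclusion depend on a second measurement and the other makes it automatic. A coordinator with a patient whose calcium has recovered at two weeks cannot satisfy both. Restarting cinacalcet follows Research Procedures and departs from Safety Precautions; excluding the patient does the reverse.

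Three things are at stake.

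- **Safety.** The protocol itself names hypocalcemia as a risk of cinacalcet (Potential Risks). Under one section a patient may be re-exposed after an event that the other section says ends participation.
- **Compliance.** Data and Safety Monitoring asks the DSMB to monitor protocol compliance. For this event the visible text supplies no single standard against which to judge it.
- **Retention.** The rule applies to treated low-turnover patients on study cinacalcet and not to their controls, so the version followed can change post-randomization losses on one side before the one-year hip QCT comparison. Research Procedures also bases adaptive randomization partly on group completion rates, so exclusions may feed into later allocation.

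**Working it through.** No sample size, power or error-rate figure is involved. The check sets the two rules side by side and follows a patient through each.

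| Step | Research Procedures | Safety Precautions |
|---|---|---|
| Trigger | Cinacalcet-induced calcium below 8.5 mg/dL | Same |
| Immediate action | Stop treatment for two weeks | Stop treatment |
| Re-measurement | At two weeks | None stated |
| Still below 8.5 mg/dL | Excluded | Excluded |
| Calcium normalized | Retained; cinacalcet restarted at half the prior dose | Excluded |
| Later check | Next monitoring visit | None stated |

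Count exclusions per affected patient (1 = excluded, 0 = retained) and subtract Research Procedures from Safety Precautions:

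- Still low at two weeks: 1 − 1 = 0. The rules differ at most in timing.
- Normalized at two weeks: 1 − 0 = 1. The rules give opposite outcomes.

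Let N be the number of study-cinacalcet patients with the event and p the fraction whose calcium has normalized at two weeks. Then

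extra exclusions under Safety Precautions = N × [p × 1 + (1 − p) × 0] = N × p.

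The documents give neither N nor p, so the product is left unevaluated. It can range from 0 (nobody recovers) to N (everybody recovers).

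Could the texts be read as one rule?

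1. *Different populations?* No. The opening clause is the same in both, so Safety Precautions cannot be confined to patients who are unable to manage on a lower dose; Research Procedures attaches its hold-and-restart path to that same clause.
2. *One section given precedence?* No visible text ranks them.
3. *Superseded wording?* Both sentences are complete current text and neither sits in a change log. Elsewhere the document shows old and new wording run together, but these two sentences show no sign of it.

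**The case against.** The strongest reply is that Safety Precautions is a condensed answer to an institutional form prompt, while Research Procedures is the operating text. There is support for this. Safety Precautions leaves out the whole hypercalcemia algorithm (10.2 to 11 mg/dL and above 11.0 mg/dL), the six-week PTH exclusion, the hold when PTH falls below 60 pg/mL, and the alendronate BSAP threshold. The reading is plausible, but it does not remove the conflict. Leaving out a rule is not the same as restating it with its condition removed. The section also writes out staged rules where it intends them: for injection-site reactions it counsels, follows up, discontinues, and ends participation only if problems persist; for gastrointestinal symptoms on alendronate it sets out hold and restart steps.

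Other objections limit the point, and they stand:

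- Both rules stop treatment at the same threshold, so the immediate response to low calcium is not in dispute.
- One-sided exclusions already arise in this group under other rules (persistent hypercalcemia, uncontrolled PTH, persistent injection-site reactions). The conflict does not create that asymmetry; it adds at most N × p cases.
- The visible text does not say whether an excluded patient is also dropped from the one-year QCT comparison. An effect on the primary endpoint is possible but not shown.
- The safety monitoring text that the DSMB is told to follow covers adverse event grading, attribution and reporting and does not mention either calcium rule. The compliance argument rests on the general remit alone.
- The Research Procedures figure and the treatment consent are not visible and might state the rule in use.

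**Conclusion.** The concern holds. The two sections contradict each other for any patient on study cinacalcet whose calcium falls below 8.5 mg/dL and has normalized at two weeks: one retains the patient and the other excludes them. For patients still low at two weeks both end in exclusion.

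The size is one patient's participation for each such recovery, N × p in total, with neither quantity given. Since both sections call the event rare, the total may well be small.

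The correction is needed because of what the rule is, a contradictory safety and withdrawal instruction in one randomized group, and not because a large numerical effect has been shown. Rarity does not tell a coordinator what to do when the event occurs. The conclusion assumes that both sentences are in force and that no unseen attachment sets an order of precedence.

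**What to change.** Reconcile the cinacalcet paragraph in Research Procedures with the matching sentence in Safety Precautions, so that one rule for calcium below 8.5 mg/dL appears in both places in identical words. The choice of rule belongs to the investigator and the DSMB; none is proposed here. When the wording is settled, check that the Research Procedures figure and the treatment consent agree with it.

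The cost is a wording amendment to one or both sections and notice to the study coordinators. No new procedures or data are needed.
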